**Postmarket Registry for Evaluation of the Superion® Spacer**

**[PRESS Registry]**

**Protocol No. 16-VIIS-01**

**PROTOCOL SYNOPSIS**

Title	Postmarket Registry for Evaluation of the Superion® Spacer
Short Title	PRESS Registry
Protocol Number	16-VIIS-01
Sponsor	Vertiflex® Inc. [name]
Registry Treatment	Superion® Indirect Decompression System (IDS)
Control Treatment	None
Registry Design	Prospective, single arm, multi-center
Registry Objective	The purpose of this postmarket surveillance registry is to gather evidence documenting the performance and clinical outcomes associated with treatment of moderate degenerative lumbar spinal stenosis using the Superion® Indirect Decompression System (IDS) .
Registry Population	Patients $\geq$ 45 years of age suffering from symptoms of neurogenic intermittent claudication secondary to a confirmed diagnosis of moderate degenerative lumbar spinal stenosis at one or two contiguous levels from L1 to L5.
Number of Subjects	A minimum of one hundred (100) patients will be enrolled in the registry.
Number of Sites	A minimum of twenty (20) sites will participate.
Registry Enrollment	Approximately 12 months for a minimum of 100 patients.
Registry Duration	Patients included in the clinical registry will return for follow-up visits at 3 weeks, and 6 and 12 months post-treatment to collect data for the primary evaluation. Registry duration is approximately 24 months based upon 12 months' enrollment plus 12 month follow-up for 100 patients. Sponsor reserves the right to enroll additional patients.
Endpoints	

VertiFlex® Patient Satisfaction Survey: A score of <math>\geq</math>3 in each questionnaire component is considered clinically significant;

Visual Analogue Scale (VAS): An improvement in back and leg pain of 20 mm (on a 100 mm scale) vs. baseline is considered clinically significant.

Achievement of Self-Defined Functional Objective. A score of <math>\geq</math>3 is considered evidence of significant improvement in function.

Other Data Collected	

Reports of serious procedure- or device-related adverse events;

Intraoperative metrics including estimated blood loss, operative time, type of anesthesia, and time to discharge.

## 1 PURPOSE

The purpose of this postmarket registry is to gather evidence documenting the performance and clinical outcomes associated with treatment of moderate degenerative lumbar spinal stenosis using the Superion® Indirect Decompression System (IDS).

[figure not shown]
## 2 PRODUCT DESCRIPTION

The Superion® Indirect Decompression System (IDS) (Superion® implant) is a spinal implant designed to treat symptoms of neurogenic intermittent claudication secondary to moderate degenerative lumbar spinal stenosis, and is implanted by minimally-invasive methods through a cannula with patient under general or local anesthesia. The implant provides indirect decompression of spinal nerves, and functions as a spinal extension-blocker to prevent compression of neural elements in extension. The device was approved by the U.S. Food and Drug Administration (FDA) for commercialization in the U.S. via PreMarket Approval (PMA) on May 20, 2015.

### 2.1 Device Description

The Superion® implant is available in five (5) sizes, from 8mm to 16mm in 2mm increments, to accommodate a range of spinal anatomy. It is composed of Titanium 6Al-4V alloy conforming to ASTM Standard Specification F136, *Standard Specification for Wrought Titanium-6 Aluminum-4 Vanadium ELI (Extra Low Interstitial) Alloy for Surgical Implant Applications*. **Figure 1** depicts the implant in its final position after placement between the spinous processes.

**Figure 1: Superion® Indirect Decompression System (IDS) *in situ***

**Lateral View**

**A/P View**

For a complete Summary of Safety and Effectiveness Data (SSED) derived from the clinical trial supporting FDA approval of the Superion® PMA, please refer to the SSED posted on the FDA website at [http://www.accessdata.fda.gov/cdrh\\_docs/pdf14/P140004b.pdf](http://www.accessdata.fda.gov/cdrh_docs/pdf14/P140004b.pdf).

The device may be implanted under general or local (e.g., conscious sedation) anesthesia. A percutaneous or mini-open approach is used for placement of a cannula via sequential dilation. A sizing tool is employed to determine the proper device size, and the Superion® implant is then inserted through the cannula and deployed under fluoroscopic guidance between spinous processes at the level to be treated. The implant serves thereafter to maintain distraction between the spinous processes while preserving motion. This maintains the intervertebral space and prevents narrowing of the canal by limiting extension at that level. Where a second, contiguous level is also symptomatic, the same procedure is used to place a Superion® implant at that level.

## **2.2 Indications for Use**

Patients will conform to indications and contraindications delineated in the Superion® labeling.

# **3 POSTMARKET SURVEILLANCE PROCEDURES**

## **3.1 Registry Design**

The PRESS registry is a prospective, single arm, multi-center registry intended to collect clinical experience with use of the Superion® Indirect Decompression System (IDS) in the treatment of moderate degenerative lumbar spinal stenosis. A minimum of twenty (20) sites will be selected to participate, enrolling a minimum of one hundred (100) patients.

Patient selection will conform to labeled indications for use, and physicians will treat patients in accordance with physician labeling and the Superion® Surgical Technique Manual. All physicians must have completed training in the use of the device provided by Vertiflex®.

## **3.2 Registry Endpoints**

Registry endpoints will include the following outcomes reflective of clinical effectiveness:

- Vertiflex® Patient Satisfaction Survey: A score of  $\geq 3$  in each questionnaire component will be deemed a clinically meaningful outcome.
- Visual Analogue Scale (VAS), Back and Leg Pain: An improvement of 20 mm (on a 100 mm scale) from baseline is considered a clinically meaningful outcome.
- Achievement of Self-Defined Functional Objective. A score of  $\geq 3$  is considered evidence of significant improvement in function.

In addition, other information to be collected will include:

- Reports of Serious Adverse Events (SAEs) determined by the Investigator to be definitely procedure- or device-related.

Perioperative information that will be collected includes:

- Type of anesthesia
- Operative time (min.)
- Estimated blood loss (cc)
- Time to discharge (hrs.)

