### **3.5.2 Intra-Operative Assessment**

Perioperative metrics will be collected and documented on the Treatment Case Report Form (Appendix B) at the time of treatment, including:

- Device size(s)
- Device lot number(s)
- Surgical level(s) treated
- Type of anesthesia
- Duration of surgery (min.), measured from start of anesthesia administration to completion of skin closure
- Estimated blood loss (cc)
- Time to discharge (hrs.), measured from completion of skin closure to discharge from treating facility

In addition, any intra-operative complications/serious adverse events deemed by the Investigator to be definitely procedure- or device-related will be documented, as described in §4.

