### **3.5.3 Post-Operative Follow-Up Assessments**

At each follow-up visit, i.e., at 3 weeks ( $\pm 2$  weeks), 6 months ( $\pm 2$  months), and 12 months ( $\pm 2$  months) post-treatment, the following information will be collected and documented on the Follow-Up Visit Case Report Form (Appendix B):

- Patient identification number and initials, and date of follow-up visit and follow-up interval (e.g., 3 weeks, 6 or 12 months, etc.) will be recorded by the Investigator and/or his/her authorized clinical research staff.
- Patients will complete a Vertiflex® Patient Satisfaction Survey. A score of  $\geq 3$  in each questionnaire component will be deemed a clinically meaningful outcome.
- Patients will complete a Visual Analogue Scale (VAS) for each leg, and for back pain. An improvement of 20 mm (on a 100 mm scale) from baseline is considered a clinically meaningful outcome.
- Patients will indicate the extent to which they have achieved their Self-Defined Functional Objective, on a 1 to 5 scale, with 1 indicating no progress at all, and 5 indicating complete achievement.

In addition, the Investigator and/or his/her authorized clinical research staff will collect and document:

- Reports of any Serious Adverse Events (SAEs) occurring since the last visit, and determined by the Investigator to be definitely procedure- or device-related.

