## 4 SERIOUS ADVERSE EVENTS (SAEs)

All Serious Adverse Events (SAEs) deemed by the Investigator to be **definitely procedure- or device-related** must be documented on the SAE Case Report Form (Appendix B).

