### 4.1 Serious Adverse Events

An adverse event is regarded as a **Serious Adverse Event (SAE)** if the injury or illness:

- A) Results in death
- B) Is life-threatening,
- C) Results in or prolongs hospitalization
- D) Results in permanent impairment of a body function or permanent damage to a body structure, or
- E) Necessitates medical or surgical intervention to preclude permanent impairment of a body function or permanent damage to a body structure.

The Vertiflex® Clinical Research group must be notified of all **Serious Procedure- or Device-Related Adverse Events** within 24 hours at:

Vertiflex®, Inc., Clinical Research  
[name] USA  
[contact]  
[contact]  
[[contact]](mailto:[contact])

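### The SAE form is required only for events judged definitely related, while the synopsis and the 24-hour rule cover related SAEs without that word; the scopes need reconciling

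*Protocol*

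**What the plan says.** Four places in the Protocol set a narrow scope for serious adverse events (SAEs):

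- Section 3.2, under other information to be collected: "Reports of Serious Adverse Events (SAEs) determined by the Investigator to be definitely procedure- or device-related".
- Section 3.5.2, for events during surgery: those "deemed by the Investigator to be definitely procedure- or device-related will be documented, as described in §4".
- Section 3.5.3, for each follow-up visit: SAEs "occurring since the last visit, and determined by the Investigator to be definitely procedure- or device-related".
- Section 4, where SAEs meeting the same threshold (in bold) "must be documented on the SAE Case Report Form".

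Two places describe the scope without *definitely*:

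- The synopsis, under Other Data Collected: "Reports of serious procedure- or device-related adverse events".
- Section 4.1, where the sponsor's "Clinical Research group must be notified of all" "Serious Procedure- or Device-Related Adverse Events" within 24 hours.

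The text shown defines no causality grades and does not say that related means definitely related. The case report forms (Appendix B) are not shown. Section 6 asks for the device and a written explanation to be sent to the sponsor after a device removal, but does not mention the SAE form.

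**The concern.** Two separate things are at issue.

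The first is the filter. An investigator who thinks an SAE may well be due to the device or procedure, but cannot be certain, has no instruction to complete the SAE form. That gap comes from the word *definitely* in sections 3.2, 3.5.2, 3.5.3 and 4.

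The second is the mismatch. The synopsis and section 3.2 describe the same data item with different scopes. Sections 4 and 4.1 attach different scopes to the form and to the notification.

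The synopsis gives the aim as follows: "The purpose of this postmarket surveillance registry is to gather evidence documenting the performance and clinical outcomes". Related SAEs are the only adverse-event data listed. The design is single-arm, so no comparator helps a reader interpret a low count. Relatedness is the investigator's call, the text shown provides for no adjudication, and monitoring is optional (section 8.3). At the stated minimums of 100 patients and 20 sites the average is 100/20 = 5 patients per site, so differing site readings could pass unnoticed. An analysis plan cannot restore events that were never put on a form.

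**Working it through.** The Protocol gives no SAE rate or precision target to reproduce. The check is mainly a comparison of text.

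**Step 1: the six statements side by side.**

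| Place | What it governs | *Definitely*? |
|---|---|---|
| Synopsis, Other Data Collected | data collected | no |
| 3.2 | data collected | yes |
| 3.5.2 | documentation at surgery, by reference to section 4 | yes |
| 3.5.3 | documentation at follow-up | yes |
| 4 | SAE Case Report Form | yes |
| 4.1 | 24-hour notification | no |

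Four carry the word and two do not.

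**Step 2: follow one event through.** Take an SAE that the investigator considers related but not definitely so.

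- Synopsis, read literally: within the data to be collected.
- 3.2, 3.5.2 and 3.5.3: not within the data to be collected or documented.
- 4: no SAE form required.
- 4.1, read literally: notify the sponsor within 24 hours.
- 6: only if the device is removed, a written explanation to the sponsor.

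The event can therefore require notification but no form, and it is inside one statement of the data scope and outside another.

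**Step 3: the alternative reading.** If the synopsis and 4.1 are short forms of *definitely related*, all six agree and the mismatch is only one of wording. The filter remains: the same event would then be neither recorded nor notified under the SAE rules.

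**Step 4: scale only.** Input: n = 100, the minimum enrolment (synopsis, 3.1, 3.3). No share of definite events among related events is assumed, because the Protocol gives none.

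- Change in the patient-level rate for each patient whose related SAE is not recorded: 1/n = 1/100 = 1.0 percentage point.
- One-sided 95% Clopper-Pearson upper limit at 0/100: 1 − 0.05^(1/100) = 0.0295, or 3.0%.
- The same limit at 1/100: solve (1 − p)^100 + 100p(1 − p)^99 = 0.05, giving p = 0.0466, or 4.7%.

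These figures show what one missed patient would do. They do not estimate how many are missed, and the effect per patient shrinks if more than 100 are enrolled.

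**The case against.** The strongest defence is that the Protocol can be read as consistent. Section 4.1 sits directly under section 4, whose opening sentence sets the scope in bold, so the phrase in 4.1 may be a short form of it. The synopsis line is a summary. Every section that governs data collection at visits or the form agrees, and the threshold looks deliberate for a single-arm registry of an approved device in which SAEs are other data and not an endpoint. No passage promises a complete SAE rate or a safety comparison.

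Much of this stands. The narrow threshold is a choice the sponsor may make, and preferring wider collection is a recommendation and not the correction of an error. The harmonised reading is plausible but not conclusive: section 4.1 says all, and nothing states that it is shorthand.

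It also stands that grades such as possible or probable are not the Protocol's terms. Appendix B may contain a relatedness scale. Even so, section 4 requires the form only for definite events, so a scale on that form would not by itself bring the others in.

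Two stronger readings are tempting and not supported. A reader might infer that nothing in the Protocol makes less-than-definite SAEs registry data. On the wider reading, the synopsis does list them under Other Data Collected; what is missing is a requirement to put them on the SAE form. A reader might also infer that the omission of *definitely* in the synopsis and 4.1 causes the gap. It does the opposite: the omission widens the scope there, and the gap comes from the word where it appears.

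**Conclusion.** The point holds as an inconsistency in scope together with a collection filter that can undercount. Read literally, a related SAE not judged definite falls within the synopsis data scope and must be notified within 24 hours, but no passage requires it on the SAE form. The recorded count of related SAEs can therefore be too low and can vary with site reading, and a count of definite events could be taken for the wider scope in the synopsis.

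The size is unknown and may be zero; it would be wrong to infer that a particular number or share of events will be lost. The 24-hour notices and explant explanations may let the sponsor recover some events, but no passage requires these to be carried onto the SAE form. The consequence is confined to the safety description. The satisfaction, pain and functional endpoints are unaffected.

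The conclusion rests on the text shown, without Appendix B, and on a literal reading of the synopsis and section 4.1. Confidence is high for the wording mismatch and lower for any practical shortfall.

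**What to change.** State one SAE scope, for both collection and notification, in the synopsis and in sections 3.2, 3.5.2, 3.5.3, 4 and 4.1.

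**Preferred.** Complete the SAE form for every SAE the investigator considers related to the device or procedure, without requiring certainty. Define a relatedness grade in the Protocol and record it on the form. Report all related SAEs by grade, with definitely related SAEs as a subset.

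**If the narrow filter is kept.** Add *definitely* to the synopsis data line, reconcile section 4.1 with section 4, and label every result *definitely related SAEs only*.

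**Cost.** Wording in six places and, if Appendix B does not already have it, one relatedness field. The preferred option brings some extra forms, some events that are in truth unrelated (patients are aged 45 or older), and possibly a less favourable count. Reporting by grade keeps those events distinguishable. The fallback costs wording only, but leaves less-than-definite SAEs off the form.

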### **3.3 Duration and Extent of Registry**

Patients included in this registry will be assessed pre-operatively for eligibility in accordance with labeled indications for use, and will return for follow-up visits at 3 weeks ( $\pm 2$  weeks), 6 months ( $\pm 2$  months), and 12 months ( $\pm 2$  months) post-treatment. Designed to enroll a minimum of one hundred (100) patients, Vertiflex® may elect to enroll additional patients.

### **3.4 Registry Population and Source of Patients**

The registry population will consist of male and female patients  $\geq 45$  years of age, with symptoms of neurogenic intermittent claudication and a confirmed diagnosis of moderate degenerative lumbar stenosis at one or two contiguous levels from L1 to L5, meeting the labeled indications for use of the Superion® Indirect Decompression System (IDS). Patients will be identified and recruited by treating clinicians and/or their designated research staff. The clinician Investigator at each site is responsible for verifying that a potential registry patient meets all eligibility criteria, as described in the labeled indications for use, and is not contraindicated.

Patients will be considered evaluable after Informed Consent has been signed, the Investigator has verified eligibility, and Vertiflex® has assigned a unique patient identifier number.

### **3.5 Registry Procedures**

Data will be collected from all patients participating in the registry pre-operatively, intra-operatively, and at follow-up visits at 3 weeks ( $\pm 2$  weeks), 6 months ( $\pm 2$  months), and 12 months ( $\pm 2$  months) post-treatment (See Visit Schedule, Appendix A). Data will be recorded on approved Case Report Forms provided by Vertiflex®. Procedures associated with individual visits are as follows:

#### **3.5.1 Pre-Operative Assessment**

The following information will be collected and documented on the Pre-Operative Assessment Case Report Form (Appendix B) by the Investigator or his/her authorized clinical research staff at the time of pre-operative assessment:

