##### Demographic Information

Date of birth, gender, height, weight, and smoking history will be collected.

Establishment of Self-Defined Functional Objective

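### Does the registry fail to collect the pre-treatment VAS that its change-from-baseline endpoint needs?

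*Protocol*

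**What the plan says.** The synopsis, section 3.2 and section 3.5.3 all define VAS success against a pre-treatment value. Section 3.2 words it as "An improvement of 20 mm (on a 100 mm scale) from baseline".

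The only readable instruction to complete the scale is in section 3.5.3, for the follow-up visits: "Patients will complete a Visual Analogue Scale (VAS) for each leg, and for back pain".

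On the pre-treatment side, section 3.5 states: "Data will be collected from all patients participating in the registry pre-operatively, intra-operatively, and at follow-up visits". It refers to Appendix A for the visit schedule and says that data go on approved forms supplied by the sponsor. Section 3.5.1 then begins: "The following information will be collected and documented on the Pre-Operative Assessment Case Report Form (Appendix B". Its readable items are confirmation of eligibility, informed consent, demographics ("Date of birth, gender, height, weight, and smoking history will be collected") and a heading on setting the functional objective, after which section 3.5.2 starts at once. Section 9 lists Appendices A and B, but their content is not in the copy reviewed.

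**The concern.** VAS is the only endpoint scored as a change from a pre-treatment value. Satisfaction is asked at follow-up only. The functional objective is set before surgery but rated only afterwards. Without a pre-operative score for back and each leg, no patient could be classed as improved by 20 mm or not. A baseline missed before surgery cannot be recovered later, by the site or at analysis.

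Read literally, the visible text seems to leave that gap. Section 3.5.1 names no pain score, and neither does the treatment-day list in section 3.5.2. The earliest VAS named falls after the implant is in place. Two other statements seem to fit the same picture. The synopsis says that patients "will return for follow-up visits at 3 weeks, and 6 and 12 months post-treatment to collect data for the primary evaluation", with no mention of a pre-operative visit. Section 3.4 makes patients evaluable without asking for a baseline score.

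**Working it through.** No protocol figure depends on this point, so there is none to reproduce. The only arithmetic is a count of what the readable text schedules:

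- Earliest named VAS: 3 weeks ± 2 weeks, so 3 − 2 = 1 to 3 + 2 = 5 weeks after treatment.
- Follow-up scores per patient: 3 scales (back, left leg, right leg) × 3 visits = 9.
- Baseline scores needed per patient: 3. Named in the readable text: 0.
- At the minimum of 100 patients: 9 × 100 = 900 follow-up scores and 3 × 100 = 300 baseline scores needed.

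These figures count mentions in the text. They do not estimate missing data. Whether the zero reflects the plan or only the copy depends on the following comparisons.

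**Where section 3.5.1 stops.** Eligibility, consent and demographics each have a heading followed by at least one sentence. The functional-objective heading has nothing under it. The list therefore appears to break off in mid-item, and any item after that heading would be lost with its text. The copy cannot show whether a VAS item followed.

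**Where a baseline VAS would be fixed.** Section 3.5 refers to Appendix A for the schedule, and section 3.5.1 refers to the pre-operative form in Appendix B. Both are named in section 9 and neither can be read here. Their absence from the copy is not an absence from the plan.

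**What the complete sentences say.** The endpoint is tied to baseline in the synopsis, section 3.2 and section 3.5.3, and section 3.5 commits to pre-operative data collection. These statements agree with each other. None says that VAS begins at 3 weeks or that no pre-operative score is taken.

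**The supporting points, one by one.**

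- *Synopsis, registry duration.* The sentence says when patients come back. A pre-operative assessment is not a return visit, so its absence from that sentence says nothing about baseline collection.
- *Section 3.4.* The rule reads "Patients will be considered evaluable after Informed Consent has been signed, the Investigator has verified eligibility", with assignment of an identifier as the last condition. It requires no outcome measurement of any kind, at baseline or follow-up, so the lack of a VAS condition does not show that the VAS is unscheduled. Handling of patients without a baseline score is commonly left to the SAP, which is not shown.
- *Section 3.5.2.* It begins "Perioperative metrics will be collected and documented on the Treatment Case Report Form (Appendix B) at the time of treatment" and lists device, surgical and discharge items. A patient-reported pain baseline would not be expected there.

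**The case for a change.** The strongest case for the concern rests on the protocol's own pattern. Section 3.5 presents its subsections as the procedures for each visit, and sections 3.5.2 and 3.5.3 name every measurement in the body text although they also cite Appendix B. By that pattern a baseline VAS belongs in the body of section 3.5.1. The one heading that survives without text concerns the functional objective, so it is no positive evidence of a VAS item. The evaluability rule in section 3.4 is complete as printed, and under it a patient with no baseline score still counts as evaluable. With at least 20 sites and monitoring only optional under section 8.3, clear visit instructions matter, and no analysis plan can restore a missed baseline.

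Part of this stands. No readable passage schedules a pre-treatment VAS, and the measurement would be irreplaceable if it were truly absent. The pattern argument, however, tells us where the item should be printed, and that is the very section whose end is cut off. Nor does it follow that a site would obtain no pre-operative score: sites work from the complete protocol and the sponsor's forms, not from the copy read here. The section 3.4 wording is a separate matter of how a term is used and leaves the question of scheduling where it was.

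**Conclusion.** The concern does not hold. The plan calls for change from baseline in three places and commits to pre-operative data collection. The apparent gap lies where the text of section 3.5.1 breaks off and where two appendices are not reproduced. Nothing in the protocol is shown to be wrong, contradictory or badly fixed on this point, and no stated figure would change. The count of 0 out of 3 baseline scores describes the readable text only. The number of patients without a baseline cannot be determined from it.

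This conclusion assumes that the bare heading at the end of section 3.5.1 reflects lost text, and that the full section, Appendix A or the pre-operative form includes the back and each-leg VAS before treatment. The first is suggested by how the other items in the section are laid out. The second is implied by the endpoint definition but cannot be confirmed here. Should the complete documents turn out to contain no pre-treatment VAS anywhere, the question would reopen.
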